12.2.4. Dose reduction

Participants should be advised to contact the relevant research nurse between the 6-monthly clinic visits/telephone calls in the event of a persistent AE that may require capsule dose reduction.

In the event that the participant experiences AEs that the treating clinician suspects to be related to trial treatment, the clinician should review the participant's treatment regimen (eg. have the capsules been taken with food?).

[figure not shown]
If the AE persists, the dose of trial treatment should be temporarily reduced as per the dose reduction algorithm in Figure 1 below. Dose reduction should be recorded in the medical notes and on the Treatment CRF.

If a participant is undergoing a course of chemotherapy and a dose reduction has stopped the symptoms of an AE, the dose should not be increased back to full dose until the course of chemotherapy has completed.

If a participant is undergoing a course of chemotherapy and has stopped taking trial capsules due to an AE (i.e. is on a treatment break), the participant should resume on the reduced dose once the course of chemotherapy has completed with a view to increasing the capsule dose to 4 capsules daily, in due course. A decision to permanently stop trial treatment should not be made during chemotherapy if possible.

If a participant is still experiencing symptoms of the AE following a dose reduction, is not undergoing a course of chemotherapy and no other factors are considered to be contributory, a permanent halt to trial treatment should be considered. If a participant does permanently stop trial treatment, a Withdrawal CRF should be completed and returned to CTRU within 24 hours. The participant should continue to attend trial visits or take a trial specific telephone call as per the trial visit schedule.

Figure 1: Dose reduction algorithm

12.2.5. Treatment Compliance

Treatment compliance will be assessed by questions at each trial visit/telephone call to determine if the participant has had any delayed, missed or modified doses. This information will be recorded on the appropriate Follow-up Form. Any unused **expired** capsules will be collected from the participants by the research team at the next trial visit or at the end of the trial for those participants undertaking telephone clinic follow up and returned to pharmacy for drug reconciliation and local destruction (see Section 11.5 above for further details).

The fatty acid analysis on visit 2 and 3 samples compared with baseline visit 1 (see Section 13.16) will act as a marker of compliance to IPE and also allows the assessment of whether the placebo arm has been 'contaminated' by possible participant supplementation with over-the-counter O3FA.

12.3 Blinding

The Principal Investigator, participating centre staff, pharmacy staff, participants and the CTRU staff involved in the day to day activities of the trial will be blinded to the treatment allocation of each participant.

Participants will not be informed of their trial allocation until the final analysis has been completed and the results of the study are published. At this time the CTRU will provide each site with a list of treatment allocations for participants recruited at that site. Participants cannot request their trial allocations until this time.

The following controls will be employed to maintain the double blind status of the trial:

- The IPE and placebo capsules and bottles will be identical in appearance and have the same labelling.
- Boxes will be identified by a unique kit code assigned at random. The CTRU Safety Statistician (an independent CTRU statistician responsible for carrying out tasks requiring access to unblinded information) will be responsible for maintaining this list, which will be securely password protected when treatment information is contained within the list.
- The Investigator and other members of the site staff involved with the trial and the participants themselves will remain blinded to the treatment allocation (except where emergency unblinding is necessitated).

The following outlines how unblinding will be kept to a minimum for tasks to be conducted unblinded at the CTRU:

- Management of kit-codes on the kit logistics application which is linked to the 24-hour randomisation system will be conducted by the CTRU Safety Statistician in addition to maintaining the back-up kit-code lists for each centre.
- Any unblinded interim reports provided to the Data Monitoring and Ethics Committee (DMEC) will be provided by the CTRU Safety Statistician and the reports will be securely password-protected.
- Suspected Unexpected Serious Adverse Reactions (SUSARs) will be unblinded by the CTRU Safety Statistician. If the event requires expedited reporting, the Safety Statistician will pass the SUSAR to the trial Data Manager who will be responsible for electronic SUSAR reporting to the Medicine and Healthcare Regulatory Agency (MHRA) and the ethics committee. Unblinded records of SUSARs reported will be maintained by the Safety Statistician.

Code break procedures are outlined below and described in detail in the Emergency Unblinding SSOP provided in the Investigator Site File and Pharmacy Site File.

12.3.1 Emergency Unblinding

Whilst the safety of participants in the trial must always take priority, maintenance of the blind is crucial to the integrity of the trial. Investigators should only break the blind when information about the participant's trial treatment is clearly necessary for the appropriate medical management of the participant and where stopping the blinded medication is not sufficient.

Unblinding may be requested on the grounds of safety by the Chief Investigator (CI), local PI or treating physician. It is anticipated that requests for unblinding will most likely originate from a participant, carer (or friend/family member) or personal physician (e.g. GP) at the time of an adverse event or planned change in non-trial related drug therapy. Requests for unblinding will first be handled by the local PI or delegate who will explore the reason for the request and evaluate the importance of knowledge of treatment assignment for participant safety. In the event of a Serious Adverse Event (SAE), all participants should be treated as though they are receiving the active medication. Refer to protocol Section 14 (Pharmacovigilance).

Should an alternative to unblinding not be identified, and if unblinding is required to optimise medical management of the participant, investigators should follow the emergency unblinding process.

Emergency unblinding is provided by the CTRU during Office Hours and the participating site pharmacy at all other times, thereby covering each 24-hour period. It is encouraged that requests for Emergency unblinding should be made directly with CTRU wherever possible.

During Office Hours (9:00 to 17:00 Monday to Friday excluding public/bank holidays, the period between Christmas Eve and New Year, Thursday afternoon before Good Friday and all Tuesdays following a bank holiday except for Mayday and New Year's Day), Investigators should telephone CTRU who will carry out the unblinding procedure.

Outside of Office Hours, or where the Investigator is unable to contact CTRU, emergency unblinding may also be undertaken by contacting the local/assigned pharmacy department at the respective participating centre who will also hold code-break envelopes. Code-Break envelopes for unblindings will be provided to pharmacy at the time of IMP delivery and each envelope will be linked to a specific box of capsules using a unique kit-code.

Direct line for CTRU emergency unblinding: [name]

The following information will be needed to perform an emergency unblinding:

- Participant details, including trial ID number, initials and date of birth
- Name of trial research site and site code
- Name of person making the request for a code-break
- Reason for requesting a code-break
- Confirmation of whether the PI authorised the request

Following the emergency unblinding of a participant, CTRU will fax or send via secure email a confirmation of emergency unblinding to the requester and the local PI. The details of the emergency unblinding should be recorded on the EMT2 Unblinding Log provided by CTRU.

Outside of Office Hours, or where the Investigator or treating physician is unable to contact CTRU, emergency unblinding must be performed by the local pharmacy department. The responsible pharmacist on duty will complete the Unblind Request CRF, retrieve the code-break information and reveal the treatment allocation to the person requesting the unblind. The pharmacist must return (by fax or secure email) the completed Unblind Request CRF to the CTRU within 24 hours of the unblinding request.

Following an emergency unblinding the participant should stop trial treatment and be treated in line with local hospital policy. The participant will continue to be followed-up as per the trial protocol.

Further information on emergency unblinding can be found in the Emergency Unblinding SSOP located within the Investigator Site File and Pharmacy Site File.

12.4 Withdrawals

In line with usual clinical care, cessation or alteration of regimens at any time will be at the discretion of attending clinicians or the participants themselves. All participants withdrawn from treatment or prescribed alternative treatment will still attend for follow-up assessments unless unwilling to do so and CRFs will continue to be completed.

The Withdrawal CRF should be completed and faxed or sent via secure email to the CTRU **within 24 hours** of the research team becoming aware.

Treatment breaks are permitted if necessary (see Section 12.2.1). Participants should not be recorded as withdrawn from trial treatment until it is clear that they will not be resuming trial treatment.

The PI or delegate should make every effort to ensure that the specific wishes of any participant who wishes to withdraw consent for further involvement in the trial are defined and documented using the Withdrawal CRF in order that the correct processes are followed by the CTRU and site following the withdrawal of consent.

It should be made clear to any participant specifically withdrawing consent for further data collection that data pertaining to safety will continue to be collected for regulatory reporting purposes and will be included in any safety analysis. In addition it is suggested that the participant is made aware of the fact that if any significant new information becomes available in regard to the treatment they have received in the trial it may be necessary to contact them in the future.

In the event that the liver metastases are not able to be removed surgically, trial treatment and follow-up should continue as per protocol (see section 13.4).

13. Assessments, Samples and Data Collection

Data will be collected using paper CRFs, the electronic templates for which will be provided by the CTRU and upon completion should be returned to the CTRU at the University of Leeds. Participating hospitals will be expected to maintain a file of essential trial documentation (Investigator Site File), which will be provided by the CTRU, and keep copies of all completed CRFs for the trial in the Investigator Site File.

The timings of interventions and assessments required for the EMT2 trial are summarised in Appendix A: Schedule of Events.

13.1 Assessment of eligibility and randomisation

Potential participants will be identified through the hepatobiliary MDT at the time of the decision to offer CRCLM surgery to that individual. The MDT will review the most recent CT of the

thorax, abdomen and pelvis and determine eligibility for CRCLM surgery. This CT scan may be collected retrospectively as part of the sarcopaenia analysis.

If the patient is eligible for CRCLM surgery, the surgeon will assess eligibility (medical review including medical history, assessment of management of the underlying disease, pregnancy and concomitant medication use) for trial participation at the surgical outpatient visit at which CRCLM surgery is discussed with the patient. The trial site team may telephone the potential participant in order to introduce the trial in general terms and then send a PIS/ICF in advance of an outpatient clinic appointment, especially if the time between outpatient review of eligibility for surgery and the date of CRCLM surgery is limited.

Participants must be screened and have given written informed consent before any trial specific procedures are performed and the participant is randomised.

For patients who do not go on to be registered, details should be added to the Screening Log (see Section 10.2). All patients who consent to trial participation must be registered.

If, following randomisation, a participant is found to be in breach of the eligibility criteria the Protocol Violations CRF should be completed and returned (by fax or secure email) to CTRU immediately.

13.2 Visit 1: Baseline Assessment and Data Collection

Trial specific assessments must take place following consent and randomisation, except for the baseline Quality of Life questionnaires which must be done following consent but should wherever possible be done **before** meeting with the clinician/randomisation.

Once randomised into the study, the participant will be assessed by a member of the research team and the following baseline assessments will be carried out:

- Participant self-reported assessments: the EQ-5D, EORTC QLQ-C30 and QLQ-LMC21 Quality of Life questionnaires and a health economics questionnaire will be administered to the participant in a Participant Questionnaire Visit 1 Pack.
- Participants should be provided with a Participant Diary Booklet to record information over the next visit period. The information collected in the booklet will be the information to be collected in the health economics questionnaire and details on compliance and adverse events. The booklet is intended to act as a reminder to the participant and must not be handed in to clinic or returned to the CTRU.
- Weight in kilograms (in light indoor clothing and without shoes).
- Blood sample for red blood cell fatty acid analysis (**for Sheffield Teaching Hospitals NHS Foundation Trust and Leeds Teaching Hospitals NHS Trust only**). A blood sample should be collected in two EDTA-coated Vacuette® tubes and agitated

immediately to prevent clotting. The blood components should be separated within 30 minutes of taking the blood sample (see Section 13.16). If not processed immediately, store the two tubes in the fridge at 4°C for up to 30 minutes.

- One box of IMP will be dispensed.
- A CT scan should be organised for 6 months following the anticipated date of CRCLM surgery, once known. For participants undergoing a two-stage resection, the CT scan should be planned for 6 months following the completion of the second resection.
- An invitation to join the Biospecimen Collection sub-study should be extended to the participant using the dedicated PISICF (see Biospecimen Collection protocol).
- If written informed consent for the Biospecimen Collection sub-study is obtained, sample collection packs should be provided and a blood sample taken (if consent given) according to the Biospecimen Collection protocol.

13.3 Research nurse telephone calls (every 2 weeks between visits 1 and 2)

Participants will be contacted every 2 weeks +/-3 days by a research nurse between randomisation and CRCLM surgery. If the research nurse is unable to contact the participant every reasonable effort will be made to contact the participant as soon as possible. The research nurse will contact the participant by telephone to perform the following assessments:

- Toxicity assessment: collection of any adverse events which may have occurred over the last two weeks.
- Details of hospital resource activity (e.g. hospital inpatient stays, outpatient clinics attending, accident and emergency attendances).
- Treatment compliance: the participant will be asked if they have missed any treatment doses in the last two weeks and for what reason.
- Details of concomitant medications including over-the-counter O3FA supplements since visit 1 or since the last research nurse telephone call. Participants should be reminded that over-the-counter O3FA supplements are prohibited.

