10.4.2 Treatment Allocation

Participants will be randomised on a 1:1 basis to receive either IPE 4 g daily or placebo and will be allocated a trial number and a unique kit-code to identify which box of capsules (active [IPE] or placebo) will be dispensed. The participant's randomisation allocation will not be disclosed in order to maintain the blinding of the trial.

A computer-generated minimisation programme that incorporates a random element will be used to ensure that treatment groups are well balanced for the following participant characteristics, details of which will be required for randomisation:

- 'Downsizing' chemotherapy prior to liver resection* (yes or no)
- Known extrahepatic CRC metastases with curative treatment planned (yes or no)
- Current regular (intention to use daily) aspirin use:

- yes to current regular aspirin use
- no to current regular aspirin use
- Add-aspirin trial participant still taking IMP (placebo or aspirin, double-blind trial so treatment allocation not required to be known at EMT2 randomisation)
- Randomising Centre
- Time between randomisation date and date of planned liver resection surgery (<2 weeks or ≥2 weeks)

*For definition see Section 9.4

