13.4 Visit 2: CRCLM surgery, Treatment Assessments and Data Collection

Participants will have a trial visit during admission on the first day of the hospital inpatient stay for CRCLM surgery. The CRCLM surgery should be <6 weeks from post randomisation.

The following assessments will be carried out:

- Toxicity assessment: collection of any adverse events which may have occurred since the last research nurse telephone call.
- Details of hospital resource activity (e.g. hospital inpatient stays, outpatient clinics attending, accident and emergency attendances).
- Participant self-reported assessments: a health economics questionnaire will be administered to the participant in a Participant Questionnaire Visit 2 Pack. It is preferable that this is administered to the participant before surgery but if this is not possible within the timeframe pre-surgery, the Visit 2 Pack may be completed during the inpatient stay.
- Participants should be provided with a Participant Diary Booklet to record information over the next visit period. The information collected in the booklet will be the information to be collected in the health economics questionnaire and details on compliance and adverse events. The booklet is intended to act as a reminder to the participant and must not be handed in to clinic or returned to the CTRU.
- Weight in kilograms (in light indoor clothing and without shoes). This may be taken from the pre-operative assessment in the clinical records.
- Blood sample for red blood cell fatty acid analysis (for Sheffield Teaching Hospitals NHS Foundation Trust and Leeds Teaching Hospitals NHS Trust only). **Please note that it is preferable that the blood sample is obtained prior to surgery, ideally on admission to hospital.** A blood sample should be collected in two EDTA-coated Vacuette® tubes and agitated immediately to prevent clotting. The blood components should be separated within 30 minutes of taking the blood sample (see Section 13.16). If not processed immediately, store the two tubes in the fridge at 4°C for up to 30 minutes.
- See Biospecimen Collection protocol if participant is in this sub-study.
- Treatment compliance: the participant will be asked if they have missed any treatment doses since the last research nurse telephone call and for what reason.

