14.3.1 Reporting of Adverse Events (AEs)

All AEs occurring **from randomisation up to 60 days after the end of trial treatment** must be recorded on the appropriate CRF. These are not subject to expedited reporting to CTRU.

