17.2 Secondary Endpoints

The secondary endpoints are:

- Overall Survival (OS), defined as the time from randomisation to death, from any cause (key secondary endpoint)
- Safety and tolerability of IPE before and after surgery, including during chemotherapy
- Patient reported quality of life, measured using the EQ-5D, EORTC QLQ-C30 and QLQ-LMC21 questionnaires
- Cost-effectiveness of IPE
- New primary cancers (excluding DCIS, cervical carcinoma *in situ*, superficial bladder carcinoma where treatment consisted of resection only and non-melanoma skin cancer where treatment consisted of resection or radiotherapy only)

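### Pre-operative calls use a fixed two-week look-back that does not match the call window, and Visit 2 has no look-back start for participants who had no call (minor)

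*Protocol*

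**What the plan says.** Section 13.3 sets the call frequency: "Participants will be contacted every 2 weeks +/-3 days by a research nurse between randomisation and CRCLM surgery". No limit is put on the delay when a call fails: "If the research nurse is unable to contact the participant every reasonable effort will be made to contact the participant as soon as possible".

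At each call the adverse event item is "Toxicity assessment: collection of any adverse events which may have occurred over the last two weeks", and for compliance "the participant will be asked if they have missed any treatment doses in the last two weeks and for what reason". The concomitant medication item in the same list is worded differently. It runs from Visit 1 or from the previous nurse call, so it leaves no gap.

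At Visit 2, on admission for surgery, Section 13.4 specifies "Toxicity assessment: collection of any adverse events which may have occurred since the last research nurse telephone call". Missed doses and concomitant or omega-3 use are asked about over the same interval. No alternative is given for a participant who had no call. Visit 3 (Section 13.5) then asks only about the time since the last trial visit.

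Three other provisions bear on this:
- Section 14.3.1 requires every adverse event to be recorded "from randomisation up to 60 days after the end of trial treatment".
- Section 12.2.5 has delayed, missed or modified doses asked about at every visit or call, with no look-back period stated.
- Section 13.2 gives each participant a diary from Visit 1 covering compliance and adverse events. It is a memory aid and is not returned.

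**The concern.** The questions that Sections 13.3 and 13.4 tell staff to put do not always span the period that Section 14.3.1 requires to be recorded. A nurse who follows Section 13.3 to the letter meets the visit instruction and can still miss part of that period. No later scheduled question recovers it, because Visit 3 starts from Visit 2.

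The data concerned have a use. "Safety and tolerability of IPE before and after surgery, including during chemotherapy" is a secondary endpoint. Section 19.6 plans a subgroup comparison by whether at least 2 weeks of trial product were received before surgery, so incomplete pre-operative dose information could matter there too.

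Surgery before any call is foreseen by the design. One minimisation factor in Section 10.4.2 is "Time between randomisation date and date of planned liver resection surgery (<2 weeks or ≥2 weeks".

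**Working it through.** The plan gives no figure to reproduce, so the check is a count of days.

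**Inputs**
- Call interval: 14 ± 3 days, i.e. 11 to 17 days (13.3).
- Look-back for adverse events and missed doses: 14 days (13.3).
- Surgery less than 6 weeks after randomisation, so day 41 at the latest (13.4).
- Visit 2 looks back to the last call (13.4), so no gap arises after the last call.

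**Formula.** Unasked days at a call = max(0, days since previous contact − 14), counting randomisation as day 0.

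**One call**
- 11 to 14 days after the previous contact: 0 unasked days.
- 17 days after: 17 − 14 = 3 unasked days.

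**Worst case with every call in window.** The text does not say whether the ± 3 days runs from the previous call or from scheduled days 14 and 28. Both readings give the same maximum.
- From the previous call: calls on days 17 and 34 give 3 + 3 = 6 days.
- From scheduled days: calls on days 11 and 31 give 0 + (20 − 14) = 6 days.
- Against the longest pre-operative period, 6/41 = 15%.

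**Average, under an assumption the protocol does not make.** Take exactly two calls, on days 14 + a and 28 + b, with a and b each equally likely from −3 to 3 (49 combinations). Unasked days = max(0, a) + max(0, b − a).
- Mean = 42/49 + 56/49 = 98/49 = 2.0 days, or 2/28 = 7% of about 28 days.
- No gap requires a ≤ 0 and b ≤ a, which is 1 + 2 + 3 + 4 = 10 combinations. Some gap therefore occurs in 39 of 49, and gaps of a single day are included in that count.

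**Late contact.** Each day beyond 14 adds one unasked day. For illustration, a first successful contact on day 21 leaves 21 − 14 = 7 days.

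**No prior call.** Surgery before day 11 precedes any in-window call, so the start point in Section 13.4 does not exist. From day 11 a call may or may not have taken place.

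**With the alternative wording.** If each contact asks back to Visit 1 or to the last completed contact, unasked days are 0 for every call timing, including surgery before any call.

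**The case against.** The general rules have no 14-day limit. Under Section 14.3.1 a nurse told of an event 16 days ago must record it. Section 12.2.5 has missed doses asked about at every contact, and the diary covers the days in question. Serious adverse events are reportable from randomisation within 24 hours of site awareness, so that duty does not depend on the call prompt. In a section about two-weekly calls, the last two weeks is naturally read as the time since the last call, and the concomitant medication item supports that intent. The CRF prompts are not among the documents and may already be right. All of this stands, and it makes the point minor. It does not remove the mismatch: Section 14.3.1 states a duty, while Sections 13.3 and 13.4 state the question put to the participant.

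A reader might infer more than the documents support:
- *That part of the pre-operative period is never asked about.* A gap arises only when contacts are more than 14 days apart and the prompt is applied as a hard cut-off.
- *That most participants have a gap.* The 39 of 49 depends on assumed timing and counts one-day gaps.
- *That participants operated on within 2 weeks have no pre-operative assessment.* They are assessed at Visit 2, with randomisation as the evident start, and some with surgery from day 11 may have had a call.
- *That the treatment comparison is biased.* The wording is the same in both blinded arms. Lost events would lower absolute counts and differences, but no distortion between arms is shown.

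**Conclusion.** The concern holds as a minor inconsistency in how pre-operative safety and compliance data are collected. Followed literally, Section 13.3 can leave up to 6 days unasked with all calls in window, and more after a late call. Section 13.4 gives no look-back start for participants operated on before any call. The 6-day maximum rests only on the protocol's call window, look-back and surgery limit. The 2.0-day mean rests on the assumed two-call, uniform timing. How many events or missed doses would actually be lost cannot be judged from the documents, since it depends on how staff apply the prompts and on what the CRFs say. PFS, OS and the sample size are unaffected.

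**What to change.** In Section 13.3, for adverse events and missed doses, replace the fixed two weeks with *since randomisation/Visit 1 or since the last completed contact*. In Section 13.4, use the same form for adverse events, missed doses and concomitant/omega-3 use. This extends the approach Section 13.3 already takes for concomitant medication. Check that the call and Visit 2 CRF prompts match, and amend them only if they do not.

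The cost is a wording change in two sections and possibly in the CRFs. No extra call, visit or staff time is needed. The only downside is a slightly longer recall period when a call is late, which the diary helps to cover.
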